An Academic Health Sciences Centre for London

Pioneering better health for all

PROTOCOL FULL TITLE: Blinatumomab in molecular relapse of AML with a t(8;21) translocation

Protocol Short Title/ Acronym: BlinAML

Version 0.6 / 19th February 2021

Trial Identifiers

EudraCT Number:	2020-002019-23
IRAS Number:	287063

Sponsor

Name of organisation(s):	Guy's and St Thomas' NHS Foundation Trust
Sponsor contact:	[name]
Address:	King's Health Partners Clinical Trials Office, [name]
[contact]
Email:	[contact]

Chief Investigator

Name:	[name]
Address:	Department of Haematology
	[name]
	[name]
[contact]
Email:	[contact]

Chief Scientific Adviser

Name:	[name]
Address:	Department of Haematology
	[name]
	[name]
[contact]
Email:	[contact]

Statistician

Name:	[name] (statistician)
Address:	Population Health Sciences, Kings College London
	[name]
	[name]
Telephone:	
Email:	[contact]

1. Study Synopsis

Title of clinical trial	Blinatumomab in molecular relapse of AML with a t(8;21) translocation.
Protocol Short Title/Acronym	BlinAML
Trial Phase if not mentioned in title	Phase II
Sponsor name	Guy's and St Thomas' NHS Foundation Trust
Chief Investigator	[name]
EudraCT number	2020-002019-23
IRAS number	287063
Medical condition or disease under investigation	Acute myeloid leukaemia (AML) with a t(8;21) translocation
Purpose of clinical trial	To determine if blinatumomab is a potential alternative to intensive chemotherapy for patients with molecular relapse of AML with a t(8;21) translocation
Primary objective	To evaluate the efficacy of blinatumomab to induce complete molecular remission
Secondary objective (s)	To evaluate: the overall incidence and severity of adverse events, the overall rate of molecular remission, duration of remission, overall survival time and healthcare resource utilization with blinatumomab
Trial design	A single arm phase II Simon's two-stage design for evaluating efficacy of blinatumomab in patients with molecular relapse or molecular persistence of acute myeloid leukaemia (AML) with a t(8;21). All enrolled patients will be statistically evaluated for the primary endpoint of molecular complete response after one cycle of treatment.
Endpoints	Primary – incidence of molecular complete remission after one cycle of treatment.
	 Secondary: Incidence of patients experiencing a grade 3 or greater non-haematological toxicity during the first cycle of treatment. Incidence of molecular complete remission at any time from trial entry Molecular relapse free survival time Overall survival time Number of days of hospital admission at 1, 3 and 6 months from entry Number of days on intravenous antibiotics or antifungals at 1, 3 and 6 months

	 Number of blood components infused at 1, 3 and 6 months.
Sample size	17 patients in total, comprising 7 in Stage I and 10 in Stage II
Summary of eligibility criteria	Confirmed first or subsequent molecular relapse or molecular persistence of AML with t(8;21) following remission induction therapy Documented CD19 expression on blasts at diagnosis or relapse. Adequate bone marrow function Age 18years or older Excluding patients with >5% blasts in BM or evidence of extramedullary relapse. Weight 45kg or greater
IMP, dosage and route of administration	Blinatumomab at 28 mcg/day per day by continuous infusion for 28 days for up to 4 cycles of therapy.
Active comparator product(s)	N/A
Maximum duration of treatment of a participant	4 cycles of 28 days each
Version and date of protocol amendments	

2. Glossary of Terms

ABPI Association of the British Pharmaceutical Industry

AE Adverse Event

ALL Acute lymphoblastic leukaemiae

ALP Alkaline phosphatase
ALT Alanine transaminase
AML Acute myeloid leukaemia

AR Adverse Reaction
AST Aspartate transaminase
BiTE Bispecific T-cell engagers
CA Competent Authority

CADD Continuous ambulatory drug delivery

CI Chief Investigator
CIV Continuous intravenous
CNS Central nervous system
CR Complete remission
CRF Case Report Form
CRP C-reactive protein

CRS Cytokine release syndrome CTA Clinical Trial Authorisation

CTCAE Common Terminology Criteria for Adverse Events

CTFG Clinical Trials Facilitation Group

CTO Clinical Trials Office

DSUR Development Safety Update Report

ECG Electrocardiogram

ECOG Eastern Cooperative Oncology Group

eCRF Electronic case report form
EEA European Economic Area
EMR Electronic medical record

EudraCT European Clinical Trials Database

FBC Full blood count GCP Good Clinical Practice

GMP Good Manufacturing Practice

HBV Hepatitis B virus

HCG Human chorionic gonadotropin

HCV Hepatitis C virus
HDAC High dose cytarabine

HIV Human immuno-deficiency virus

HSCT Haematopoietic stem cell transplantation

The lymphoid marker CD19 is also aberrantly expressed on over 80% of acute myeloid leukaemia patients (AML) with the t(8;21) fusion⁸⁻¹⁰, providing a rationale for blinatumomab use in this condition. In a recent report, a patient with a CD19 positive relapsed t(8;21) AML achieved a complete molecular response after blinatumomab therapy¹¹. AML with a t(8;21) translocation accounts for approximately 8-10% of cases in younger adults (age <60 years)¹⁵, and is generally regarded as a favourable risk sub-type of AML as there is a cure rate of approximately 60-65% with standard AML chemotherapy¹⁶. However, relapse still occurs in about one third of patients, requiring further salvage chemotherapy and bone marrow transplantation as a standard of care^{1,2}. Some patients may have multiple relapses even post-transplant¹⁶.

The *RUNX1-RUNX1T1* fusion generated by the t(8;21) can be detected and monitored by real time quantitative PCR (RT-qPCR)¹⁷⁻¹⁹ and it is established practice in the UK to undertake regular monitoring of minimal residual disease status using RT-qPCR methodology on bone marrow samples taken following each cycle of induction and consolidation chemotherapy and for two-three years following completion of chemotherapy. Thus, in UK practice relapse or persistence of disease is mainly detected and treated at the molecular level prior to any overt haematological relapse. This gives the possibility of earlier intervention at the level of molecular relapse for patients with rising transcript levels before overt haematological relapse occurs. Earlier intervention may improve response rate and may be better tolerated than salvage treatment at haematological relapse^{17,18}.

The prognosis for patients with AML who relapse following intensive chemotherapy is generally poor and established treatments are highly suboptimal in terms of efficacy, side effects, cost and quality of life²⁰. Allogeneic haematopoietic stem cell transplantation (HSCT) is a potentially curative treatment but not all patients are able to reach transplant and even for those who do, long-term survival is only 40-50%. For example, in the relapse arm of the NCRI AML17 trial, a second complete remission (CR2) was achieved in 74% of patients but only

57% received a transplant, resulting in 5-year overall survival in the whole cohort of 22%. Reasons for not going to transplant include resistant disease and toxicity of the salvage chemotherapy employed²¹.

The standard approach for molecular relapse of AML with t(8;21) is intensive salvage chemotherapy^{1,2}, a commonly used regimen being FLAG-lda²¹. The FLAG-lda salvage chemotherapy regimen is delivered as an in-patient and results in prolonged cytopenias requiring a prolonged in-patient stay (median of 32 days in the NCRI AML17 trial). Critical care admission is required in ~10% of patients. Supportive care requirements are high and patients required a median of 10.4 units of blood, 12.9 units of platelets and 19.3 days of IV antibiotics in the AML17 trial. 60 day mortality in this trial was 6%²¹.

For AML with t(8;21) one or two course of salvage chemotherapy is routinely given to patients with molecular persistence or relapse, as these patients will inevitable progress to a full haematological relapse without intervention. MRD monitoring in the UK for both adults and children is provided by the Cancer Genetics Service at Guy's Hospital, London. Samples are analysed and results and clinical advice given in accordance with European LeukaemiaNet guidelines¹⁸.

For patients with molecular relapse, MRD continues to be monitored and is used to track response to salvage chemotherapy and inform timing of transplant and post-transplant intervention. The advantage of this approach is that treatment can be initiated well before a full relapse has occurred when the patient is well and has normal blood counts.

Current treatment for molecular relapse is identical to that for haematological relapse, this is due to the lack of other effective treatment options until now. The development of blinatumomab offers the potential to deliver effective therapy to patients with a molecular relapse and without the need for debilitating intensive in-patient salvage chemotherapy. This approach would offer dramatic improvements in patient experience, quality of life and resource use and provides a potential window of opportunity for outpatient-based therapy.

4. Trial Objectives and Design

4.1. Trial Objectives

In this study we propose to evaluate the safety and efficacy of blinatumomab for up to 4 cycles of therapy in patients with confirmed molecular relapse of t(8;21) positive AML.

The primary objective is to evaluate the efficacy of blinatumomab to induce complete molecular remission (MRD negativity) in patients with molecular relapse or persistence of AML with t(8:21), after one cycle of treatment.

Secondary objectives:

- To evaluate overall survival in patients with molecular relapse or persistence of AML with t(8;21) translocation treated with blinatumomab
- To evaluate the effect of blinatumomab on duration of MRD negativity
- To evaluate the effect of blinatumomab on the kinetics of MRD
- To evaluate resource utilization
- To evaluate the incidence of patients experiencing a grade 3 or greater nonhaematological toxicity during the first cycle of treatment.

4.2. Primary endpoints

 Achievement of a molecular complete response defined by absence of detectable RUNX1-RUNX1T1 fusion transcripts after one cycle of treatment with blinatumomab.

4.3. Secondary endpoints

- Incidence of patients experiencing a grade 3 or greater non-haematological toxicity during the first cycle of treatment.
- Incidence of molecular complete remission at any time from trial entry (evaluated at end of trial)
- Molecular relapse free survival time (evaluated at end of trial)
- Overall survival time (evaluated at end of trial)
- Number of days of hospital admission at 1, 3 and 6 months from entry
- Number of days on intravenous antibiotics or antifungals at 1, 3 and 6 months
- Number of blood components infused at 1, 3 and 6 months

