4.5. Schedule of events

	Screening (within 21							Cycl	es 1 to	4					90 days	2-Year Follow-	NACAL -I
	days prior to treatment)	Day 1*§	Day 2§	Day 3	Day 4	Day 8 (+/- 2d)	Day 11	Day 15 (+/- 2d)	Day 18	Day 22 (+/- 2d)	Day 25	Day 29 (+/- 2d)	Days 30-42 (+ 7d)	Unschedule d visit	after last treatment (+/- 5d)	up Period ^	Withdrawal visit
Informed consent	X																
Eligibility assessment	Х																
Medical history	Х																
Physical exam,vital signs and temperature	х	х	х	Х		Х		Х		Х		Х		Х	Х	Х	х
Neurological exam and writing test	Х	Х	Х	Х		Х		Х		Х		Х		Х	Х		Х
ECOG performance status	Х															Х	
ECG	Х														Х		Х
Urinalysis	Х	Х	Х	Х		Х		Х		Х		Х			Х	Х	Х
Pregnancy test (if applicable)	Х														Х		Х
Haematology and biochemistry	Х	Х	Х	Х		Х		Х		Х		Х		Х	Х	Х	Х
Virology (HIV, HBV, HCV)	Х																
Serum immunoglobulins	Х											Х			Х		Х

	' after last													2-Year Follow-	With drawal		
	days prior to treatment)	Day 1*§	Day 2§	Day 3	Day 4	Day 8 (+/- 2d)	Day 11	Day 15 (+/- 2d)	Day 18	Day 22 (+/- 2d)	Day 25	Day 29 (+/- 2d)	Days 30-42 (+ 7d)	Unschedule d visit	treatment (+/- 5d)	up Period	Withdrawal visit
Bone Marrow aspirate (+/- trephine)	Х											X ⁺				Х	
Response assessment												Х					
Blinatumomab infusion			Continuous infusion days 1 – 28 of each cycle Treatment break														
CADD pump attendance#		х			х	х	х	х	х	х	х	х					
Concomitant medications	Х		<< Ongoing assessment >>														
Adverse events			<< Ongoing assessment until 90 days after treatment discontinuation >>								X						
Supportive Care Requirements						<<	Ongoi	ng assessi	ment ur	ntil treatme	nt disco	ontinuation	>>				Х

NOTES:

Data on concomitant medications, adverse events and supportive care requirements may be collected during unscheduled visits

[figure not shown]
§ indicates inpatient visits. All other scheduled visits are outpatient visits.

*Clinical assessments and laboratory assessment performed within 3 days prior to the first dose of blinatumomab will not have to be repeated on day 1 cycle 1

^For patients who did not undergo allogeneic HSCT, Efficacy follow-up visits for assessment of molecular relapse and until haematological relapse will take place 3-monthly (calculated from cycle 1 day 1) within the first year and 6-monthly within the second year until completion of a 2-year period after treatment with blinatumomab. Telephone follow-up will be performed for patients who have undergone HSCT.

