7.1. Screening

7.1.1. Eligibility Screening Period

Written informed consent must be obtained from each patient at or prior to the start of the 21-day screening period and before performance of any study-specific procedure. Standard of care MRD samples may be analysed prior to screening or enrolment onto this clinical trial.

All patients who have signed the Informed Consent Form (ICF) will be recorded on the Subject Screening Log. The patient is considered as being enrolled onto the study once written informed consent has been obtained. The eligibility screening period starts with the first study specific assessment after the ICF has been signed by the patient. Each patient will be assigned a unique patient identification number. If a patient is screened but not treated, the reason should be recorded. That patient's number will not be re-used.

Clinical assessments and laboratory assessment performed within 3 days prior to the first dose of blinatumomab will not have to be repeated on day 1 cycle 1. All results will be available before a patient will be declared eligible for study participation.

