7.2. Treatment Period (Cycle 1 - 4)

Patients will be hospitalised during at least the first three days of the first cycle and during at least the first two days of each following cycle. Before starting the infusion of blinatumomab, the patient will be examined physically and blood samples for safety laboratory parameters will be taken. For starting the study treatment the laboratory results will not have to be awaited.

Following the start of the infusion AE/SAE and concomitant medication will be evaluated continuously throughout the whole study until the 90-day visit. After the 90-day visit, only (S)AEs potentially related to blinatumomab should be documented in the CRF (and reported to the sponsor, if applicable). In addition, only anti-leukemic concomitant medication and medication related to blinatumomab related (serious) adverse events should be documented in the CRF. The vital signs and the laboratory tests will be repeated on D2 and D3 and at each visit during the treatment period.

Replacement of infusion bags will be performed as described in the Operations Manual. CADD pump infusion bags will be changed twice a week. To account for weekends and bank holidays, this will be on Tuesdays and Fridays. Each treatment cycle should begin on a Tuesday.

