8.2. Procedures for Assessing Efficacy Parameters

RT-qPCR analysis on the bone marrow aspirate performed on day 29 of cycle 1 will be used to assess the primary endpoint. Verification of receipt of a sufficient sample by the central MRD lab is a rate limiting step for determination of eligibility and potential protocol treatment.

Procedures for assessment of secondary endpoints will include

- Regular and unscheduled clinical assessments for AEs/SAEs as outlined in section 7
- RT-qPCR on bone marrow aspirates performed at the end of each treatment cycle
- Follow-up assessments (refer to section 7.3) to assess for relapse and survival
- Review of CRFs and patient medical notes to assess days of hospital admission, antibiotic and antifungal use and blood component transfusions

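### Resource-use endpoints run to 6 months, but scheduled supportive-care collection stops at treatment discontinuation and the notes review that might fill the gap has no stated window

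*Protocol*

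**What the plan says.** Resource utilisation is a secondary objective (Protocol 4.1). Section 4.3 turns it into three endpoints. The one for admissions is "Number of days of hospital admission at 1, 3 and 6 months from entry"; anti-infective use is counted as "Number of days on intravenous antibiotics or antifungals at 1, 3 and 6 months", and transfusion as "Number of blood components infused at 1, 3 and 6 months". Only the first names a starting point, and the protocol does not define entry for these counts. Section 7.1.1 says: "The patient is considered as being enrolled onto the study once written informed consent has been obtained". Follow-up visits, by contrast, are timed from cycle 1 day 1 (4.5 and 7.3.2).

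The schedule in section 4.5 has a row headed "Supportive Care Requirements". It is an ongoing assessment that ends when treatment is discontinued, with one further mark at the withdrawal visit. The adverse-event row above it continues to 90 days after discontinuation. A note adds an option: "Data on concomitant medications, adverse events and supportive care requirements may be collected during unscheduled visits".

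Two other places bear on these data. Section 7.2 says: "Following the start of the infusion AE/SAE and concomitant medication will be evaluated continuously throughout the whole study until the 90-day visit". After that visit, medication goes into the CRF only if it is anti-leukaemic or given for a blinatumomab-related event. Section 8.2 gives the method for the endpoints: "Review of CRFs and patient medical notes to assess days of hospital admission, antibiotic and antifungal use and blood component transfusions". It states no period for that review.

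**The concern.** An endpoint counted to 6 months needs every patient observed to 6 months or death. Here the dedicated collection period is tied to treatment, and treatment length varies by design. Section 5.5 allows one to four cycles and lets a patient go to allogeneic transplant after one. Section 5.9 stops treatment for relapse, molecular progression or adverse events. If sites follow the schedule, a patient who stops after one cycle has a much shorter recorded period than one who completes four. Days and units used after stopping would go uncounted, and they would look like zeros.

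The undefined start adds a second problem. Counting from consent or from the first dose changes how much treatment falls inside each window, most of all the 1-month window.

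An analysis plan could not repair this later, because the data would not have been collected. At stake is whether the three counts describe resource use over the stated periods or only while on treatment.

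**Working it through.** **Inputs.** Infusion 28 days, infusion-free interval 14 days, extendable by up to 7 days; one to four cycles (5.5). Screening up to 21 days before treatment (4.5). Adverse-event interruption of up to 7 days within a cycle, with the same cycle then continued to 28 infusion days (5.7). Safety visit 90 days after the end of infusion (7.3.1). Six months taken as 6 × 30.44 = 182.6, rounded to 183 days; three months as 91 days.

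**The plan's own figure.** 28 + 14 = 42 days = 6 weeks, so day 43 is day 1 of the next cycle, as sections 5.5 and 7.2.1 state.

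**Scheduled supportive-care collection, counted from cycle 1 day 1, cycles on schedule.** Last infusion day after c cycles = 42 × (c − 1) + 28. Gap to 6 months = 183 − that day.

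| Cycles | Last infusion day | Gap to day 183 | Gap to day 91 | Last infusion day + 90 | Gap to day 183 |
|---|---|---|---|---|---|
| 1 | 28 | 155 | 63 | 118 | 65 |
| 2 | 70 | 113 | 21 | 160 | 23 |
| 3 | 112 | 71 | none | 202 | none |
| 4 | 154 | 29 | none | 244 | none |

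Columns 3 and 4 apply to the supportive-care row. The last two columns apply to adverse-event and concomitant-medication recording, and are shorter if the safety visit is brought forward for transplant (7.3.1).

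**If treatment is taken to end with the six-week cycle**, the row stops on day 42, 84, 126 or 168. The gaps to day 183 become 141, 99, 57 and 15 days.

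**Latest plausible end after four cycles.**
- From consent, 21 days of screening: 154 + 21 = day 175, 8 days short.
- From day 1, three 7-day extensions: 154 + 21 = day 175, 8 days short.
- From consent, screening and extensions together: 154 + 21 + 21 = day 196, past 6 months.
- From day 1, a 7-day interruption in each cycle: 154 + 28 = day 182, about 6 months.
- From consent, all three: 154 + 21 + 21 + 28 = day 224.

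**Effect of the start date on the 1-month count.** From day 1, a 30-day window holds all 28 infusion days. From consent with 21 days of screening, it holds 30 − 21 = 9.

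**Other streams, by endpoint.**
- Blood components: neither visit list in section 7.3 contains transfusions. The telephone collection in 5.5 does, but it begins only after the two-year follow-up.
- IV anti-infectives: captured as concomitant medication to the 90-day visit. After it, those unrelated to blinatumomab events leave the CRF.
- Admission days: unplanned admissions can surface as SAEs to the 90-day visit. Preplanned and elective admissions are not SAEs (note under 9.2), and events that are outcome measures are exempt (9.5). After transplant, the contact in 7.3.2 covers relapse-free and overall survival, conditioning, donor type and transplant mortality, but not admissions.

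**The case against.** The strongest reply is that section 8.2 names the data source for exactly these three items and sets no cut-off. The endpoint itself supplies 1, 3 and 6 months, and section 16 makes the electronic medical record source data. On that reading the schedule row is only one input, and a notes review can reach 6 months for everyone. This is why a reader who infers that no patient is covered to 6 months goes too far. The medication and adverse-event stream also passes day 183 after three or four on-schedule cycles, and a four-cycle patient counted from consent with prolonged intervals can pass it on the supportive-care row alone.

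A reader might also infer that early stoppers will look cheapest and that this flatters blinatumomab against the FLAG-Ida figures in section 3. The document does not support that. It does not say that early stoppers use the most care, plans no between-group comparison (10.2), and gives the FLAG-Ida figures as background rather than as comparators for these endpoints.

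What remains is that 8.2 relies partly on the CRF, and the schedule tells sites to stop supportive-care entries at discontinuation. The notes half has no window. Patients are referred by their treating teams (6.3), so some later care may be recorded at other hospitals. The protocol neither says that those records are unavailable nor provides for obtaining them for these endpoints. The later telephone collection in 5.5 does not reach back to the first 6 months.

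**Conclusion.** The mismatch stands and should be corrected. On the supportive-care row alone, with on-schedule cycles counted from cycle 1 day 1, the uncollected part of the 6-month window is about 155, 113, 71 or 29 days after one, two, three or four cycles. It is 14 days less in each case if treatment is taken to end with the six-week cycle. The shortfall grows the earlier treatment stops, so any resulting undercount is differential: it falls on patients who relapse, stop for toxicity or go to transplant.

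How far this biases the counts downward depends on how complete the notes review proves to be, which the protocol does not fix. It is a risk, not a certainty, and its direction relative to chemotherapy cannot be stated. The figures assume the patient is alive at 6 months and take the schedule row as the text gives it; its column span could not be checked. These are descriptive secondary endpoints, and neither the primary endpoint nor the two-stage rule is affected.

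**What to change.** Reconcile Protocol sections 4.3, 4.5 and 8.2:

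- Extend the supportive-care row and the matching CRF pages to 6 months for every patient, regardless of treatment or transplant status.
- State in 8.2 that the notes review covers the same period, including care at other hospitals where obtainable.
- Name one start date for all three endpoints and all three time points. Cycle 1 day 1 would match the follow-up visits. If consent is kept, say so, because the 1-month count then includes screening.

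The cost is a wording and CRF change, plus modest extra notes or telephone collection for about 17 patients.
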